### 8.2.2 Secondary Efficacy Analysis

The onset of efficacy, based on the SKAMP total scores, will be defined as the time of the first assessment time showing statistical significance between d-ATS and placebo. If no significant difference is found at any time point for the onset of efficacy, no onset of efficacy will be deemed to have occurred, and the onset of efficacy will be defined as 'none'. Onset of efficacy as measured by the SKAMP total score will be analyzed using the same MMRM model as for the primary analysis.

To preserve the Type I error rate in analyzing these endpoints of onset and duration of efficacy, a closed test procedure will be used. The closed test principle states that the trial-wise error rate can be controlled by the ordered testing of each hypothesis in the closed family using a suitable  $\alpha$  level significance. A condition of the Closed Test procedure is that the order of testing of the endpoints in a family matters. Thus hypotheses in a family must be ordered and the testing of each subsequent hypothesis in the order can only proceed if the testing of the prior hypothesis achieves a significant p-value with Type I error rate of predetermined  $\alpha$  level, which will be set at  $\alpha = 0.05$  for this study. Testing of the hypotheses in the family proceeds until a hypothesis fails to achieve a significant p-value. If/when a hypothesis in the family fails to achieve significance, then significant p-values cannot be claimed for all subsequent hypotheses in that family, i.e., once one hypothesis fails to achieve significance, testing should cease.

If the primary efficacy endpoint, difference between d-ATS and placebo in mean SKAMP total score for the double-blind phase, is statistically significant (i.e.,  $p < 0.05$ ), the secondary variables of onset and duration of efficacy will be tested using a closed testing procedure. The closed testing procedure starts from the time-point of 1 hour post-morning dose, then 2, 3, 4.5, 6, 7, 9, 10 and 12 hours post-dose. At each timepoint the order of testing will be onset of efficacy followed by duration of efficacy, before moving to the next timepoint. Duration of efficacy will not be considered until onset of efficacy has been determined.

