5. DEFINITIONS

SKAMP Total Score

The SKAMP total score will be the sum of the 13 individual item scores at each timepoint. Missing data will not be handled at an item level, if any of the 13 items are missing for a timepoint then the SKAMP total score will be missing for that timepoint.

Mean SKAMP Total Score

The mean SKAMP total score will be the average of all SKAMP total scores collected over the course of a laboratory assessment day, with the exception of the score from the session prior to dosing.

Onset of efficacy

The onset of efficacy, based on the SKAMP total scores, will be defined as the time of the first assessment time showing statistical significance between d-ATS and placebo. If no significant difference is found at any time point for the onset of efficacy, no onset of efficacy will be deemed to have occurred, and the onset of efficacy will be defined as 'none'.

Duration of efficacy

The duration of efficacy, based on the SKAMP total scores, will be defined as the difference between the time point that indicates that the effect has ended and the onset of efficacy, as defined above. The time point that indicates that the effect has ended will be defined as the first time point at which there is a non-significant difference between the two treatment groups after a time point in which there is a significant difference between the two treatment groups. If there is no time point at which there is a non-significant difference between the two treatment groups after a time point in which there is a significant difference between the two treatment groups, then the end of effect will be defined as 12 hours post-dose.

Onset of effect (50% reduction in SKAMP total score)

Onset of effect of 50% reduction in SKAMP total score is defined for each subject as the first time point at which there is a 50% reduction in SKAMP total score from the pre-dose observation on the same classroom day.

Duration of effect (50% reduction in SKAMP total score)

Duration of effect of 50% reduction in SKAMP total score will be determined by persistence of the 50% reduction from the pre-dose observation in SKAMP total score level. The end of effect will be determined as the first timepoint after onset of effect at which 50% reduction from the pre-dose observation in SKAMP total score is not observed. The duration of effect will be calculated as the difference between the end of effect and onset of effect, in hours.

Age

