To preserve the Type I error rate in analyzing the secondary endpoints of onset and duration of efficacy, a closed test procedure will be used. The closed test principle states that the trial-wise error rate can be controlled by the ordered testing of each hypothesis in the closed family using a suitable α level significance. A condition of the Closed Test procedure is that the order of testing

of the endpoints in a family matters. Thus hypotheses in a family must be ordered and the testing of each subsequent hypothesis in the order can only proceed if the testing of the prior hypothesis achieves a significant p-value with Type I error rate of predetermined α level, which will be set at $\alpha= 0.05$ for this study. Testing of the hypotheses in the family proceeds until a hypothesis fails to achieve a significant p-value. If/when a hypothesis in the family fails to achieve significance, then significant p-values cannot be claimed for all subsequent hypotheses in that family, i.e., once one hypothesis fails to achieve significance, testing should cease.

If the primary efficacy endpoint, difference between d-ATS and placebo in mean SKAMP total score for the double-blind phase, is statistically significant (i.e., $p<0.05$), the secondary variables of onset and duration of efficacy will be tested using a closed testing procedure. The closed testing procedure starts from the time-point of 1 hour post-morning dose, then 2, 3, 4.5, 6, 7, 9, 10 and 12 hours post-dose. At each timepoint the order of testing will be onset of efficacy followed by duration of efficacy, before moving to the next timepoint. Duration of efficacy will not be considered until onset of efficacy has been determined.

All data collected will be presented in data listings, and the listings will be sorted by investigator/site, subject, and time point.

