7.1.3 Secondary Variables

7.1.3.1 SKAMP

The onset of efficacy, based on the SKAMP total scores, will be defined as the time of the first assessment time showing statistical significance between d-ATS and placebo. If no significant difference is found at any time point for the onset of efficacy, no onset of efficacy will be deemed to have occurred, and the onset of efficacy will be defined as 'none'.

Onset of efficacy as measured by the SKAMP total score (defined in Section 5) will be analyzed using the same MMRM model as for the primary analysis. In the model, the SKAMP total scores for each timepoint will be analyzed with the fixed effects of sequence (two levels), period (two levels), treatment (two levels) and time (10 levels, one for each of 30 minutes prior and 1, 2, 3, 4.5, 6, 7, 9, 10, and 12 hours post dosing) while the repeated effect will be defined for subject-within-sequence. The interaction term for treatment * time will be included in the model, but not tested for significance. The example SAS code shown in section 7.1.1 may be used for this analysis, substituting the estimate statement given (mean estimates across timepoints) for the following set of statements (mean estimates at each timepoint):

```
estimate 'd-ATS - Placebo 1hr post dose'  
<treatment> -1 1  
<treatment*timepoint> 0 -1 0 0 0 0 0 0 0 0 0 0 0 0 0 0 0 0 0 0 0  
/ cl;  
  
estimate 'd-ATS - Placebo 2hrs post dose'  
<treatment> -1 1  
<treatment*timepoint> 0 0 -1 0 0 0 0 0 0 0 0 0 0 0 0 0 0 0 0 0 0  
/ cl;  
  
estimate 'd-ATS - Placebo 3hrs post dose'  
<treatment> -1 1  
<treatment*timepoint> 0 0 0 -1 0 0 0 0 0 0 0 0 0 0 0 0 0 1 0 0 0 0 0  
/ cl;  
  
estimate 'd-ATS - Placebo 4.5hrs post dose'  
<treatment> -1 1  
<treatment*timepoint> 0 0 0 0 -1 0 0 0 0 0 0 0 0 0 0 0 0 0 1 0 0 0 0  
/ cl;  
  
estimate 'd-ATS - Placebo 6hrs post dose'  
<treatment> -1 1  
<treatment*timepoint> 0 0 0 0 0 -1 0 0 0 0 0 0 0 0 0 0 0 0 0 1 0 0 0  
/ cl;  
  
estimate 'd-ATS - Placebo 7hrs post dose'  
<treatment> -1 1  
<treatment*timepoint> 0 0 0 0 0 0 -1 0 0 0 0 0 0 0 0 0 0 0 0 0 1 0 0 0
```

```
estimate 'd-ATS - Placebo 9hrs post dose'  
<treatment> -1 1  
<treatment*timepoint> 0 0 0 0 0 0 0 -1 0 0 0 0 0 0 0 0 0 1 0 0  
/ cl;  
  
estimate 'd-ATS - Placebo 10hrs post dose'  
<treatment> -1 1  
<treatment*timepoint> 0 0 0 0 0 0 0 0 -1 0 0 0 0 0 0 0 0 0 1 0  
/ cl;  
  
estimate 'd-ATS - Placebo 12hrs post dose'  
<treatment> -1 1  

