<treatment*timepoint> 0 0 0 0 0 0 0 0 0 -1 0 0 0 0 0 0 0 0 0 0 1  
/ cl;
```

The two treatment levels will be: d-ATS (5, 10, 15, 20 mg doses combined) and placebo. Continuous summary statistics will be presented for the SKAMP total score at each time point for Visits 6 and 7 for the FAS population. Raw means, LS means, differences in LS means, and 95% CI for the difference between treatment arms, and p-values will be calculated for each post-dose time point and for mean score over the treatment day for the FAS population.

The SKAMP total scores will also be plotted by time point for the FAS population.

Scaled residual and random effects plots will be considered to check the assumptions behind the mixed model.

The assessment of treatment differences will follow the closed testing procedure described in Section 7. The closed testing procedure starts from the time-point of 1 hour post-morning dose, then 2, 3, 4.5, 6, 7, 9, 10 and 12 hours post-dose. At each timepoint the order of testing will be onset of efficacy followed by duration of efficacy, before moving to the next timepoint. Duration of efficacy will not be considered until onset of efficacy has been determined.

- The onset time of efficacy action will be determined as the first post-dose time where the difference between the two treatments is statistically significant (i.e., $p \leq 0.05$).
- If the difference between the two treatments is statistically significant (i.e., $p \leq 0.05$) at the 1 hours post-dose time point, the duration of efficacy will be claimed as the difference in hours between the end of efficacy; the last consecutive time point at which the difference is still statistically significant (i.e., $p \leq 0.05$) and onset of efficacy. If there is no time point at which there is a non-significant difference between the two treatment groups after a time point in which there is a significant difference between the two treatment groups, then the end of efficacy will be defined as 12 hours post-dose.

For example, if a statistically significant difference in mean SKAMP total scores for d-ATS vs. placebo was determined at 1 hour post-dose and statistical significance was measured at all time-points up to and including 10 hours post-dose, but statistical significance was not reached at 12 hours post-dose, onset of clinical efficacy and end of clinical efficacy would be defined as 1 hours post-dose and 10 hours post-dose, respectively, with duration of efficacy being 9 hours.

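### The SKAMP stopping rule and the definition of onset are not reconciled when 1 h fails and a later time is significant, and the SAP has two different end-of-effect rules

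*SAP*

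**What the plan says.** **Testing order.** Protocol 8.2.2 states: "The closed testing procedure starts from the time-point of 1 hour post-morning dose". It then moves through 2, 3, 4.5, 6, 7, 9, 10 and 12 h, and SAP 7 repeats this order. Each step uses 0.05, testing opens only if the primary comparison is significant, and "once one hypothesis fails to achieve significance, testing should cease". After a failure, nothing later in the family may be claimed as significant. Within a time point onset comes before duration, and "Duration of efficacy will not be considered until onset of efficacy has been determined".

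**Onset.** SAP 5 says that onset "will be defined as the time of the first assessment time showing statistical significance between d-ATS and placebo". SAP 7.1.3.1 and Protocol 8.2.2 carry the same definition. The result none is tied to one condition: "If no significant difference is found at any time point for the onset of efficacy". SAP 7.1.3.1 also says that treatment differences will be assessed by the SAP 7 procedure, and then adds: "The onset time of efficacy action will be determined as the first post-dose time", meaning the first with a significant difference.

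**Duration.** SAP 5 measures from onset, whatever its time, to the end of effect. The point showing that the "effect has ended will be defined as the first time point at which there is a non-significant difference" following a significant one, or 12 h if significance never lapses. SAP 7.1.3.1 words it differently. If the treatments differ significantly "at the 1 hours post-dose time point, the duration of efficacy will be claimed as the difference in hours" between onset and the last time in the unbroken significant run. Its worked example is significant from 1 to 10 h and not at 12 h, with a duration of 9 h. Protocol 8.2.2 does not define how duration is calculated.

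**Use of the result.** SAP 7.1.3.1 repeats the primary analysis as a sensitivity analysis, leaving out times before onset and after the last time counted in the duration.

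**The concern.** Read literally, a chain that starts at 1 h and stops at the first failure can return only a 1 h onset or no claim. A definition of onset as the first significant time, with none reserved for the case where nothing is significant, can return any of the nine post-dose times. If the drug takes longer than an hour to separate from placebo, the plan offers two answers from one set of p-values and does not say which to report. A choice made after unblinding could be driven by the result.

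The two end-of-effect rules cause a similar problem for duration. Both choices also determine which data enter the sensitivity analysis limited to the efficacy window.

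**Working it through.** **1. Reproduce the plan's own figure.** In the SAP 7.1.3.1 example, onset is 1 h and the last consecutive significant time is 10 h, so duration = 10 − 1 = 9 h, as stated. Both the stopping rule and the onset definition return a 1 h onset here, so the example does not show which one governs when they differ.

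**2. When the two onset rules differ.** Each of the nine post-dose times is either significant or not, giving 2^9 = 512 patterns.
- If 1 h is significant, both rules give a 1 h onset.
- If nothing is significant, both give none.
- The remaining patterns have 1 h failing and at least one later time significant: 2^8 − 1 = 255 patterns. Here the stopping rule gives no claim and the definition gives a later onset.

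This is a count of logical possibilities, not a probability. It shows that the condition is exact.

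**3. A case.** Take p=0.20 at 1 h and p<0.001 at 2 to 12 h.
- Stopping rule: the 1 h test fails, testing ends, and no onset or duration is claimed.
- Definition: onset is 2 h. Significance never lapses, so the effect ends at 12 h and the SAP 5 duration is 12 − 2 = 10 h.
- SAP 7.1.3.1 states no duration, because its rule is conditional on significance at 1 h.
- Sensitivity analysis: under the definition it drops pre-dose and 1 h and keeps eight post-dose times (2, 3, 4.5, 6, 7, 9, 10, 12 h). Under the stopping rule there is no onset, and the data set is undefined.

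**4. The two end-of-effect rules.** This step needs no assumption.

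| Pattern | SAP 5 duration | SAP 7.1.3.1 duration |
|---|---|---|
| Significant 1 to 10 h, not at 12 h | 12 − 1 = 11 h | 10 − 1 = 9 h |
| Significant 1 to 12 h | 12 − 1 = 11 h | 12 − 1 = 11 h |

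SAP 5 cannot tell these two cases apart. SAP 7.1.3.1 can.

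**The case against.** The best defence is that the closed procedure governs. SAP 7.1.3.1 says, just before its onset rule, that the SAP 7 procedure will be followed. In the onset definition, significant can then mean significant within that procedure, so onset is 1 h or none. The SAP 7.1.3.1 duration rule, conditional on 1 h, fits this reading. It is coherent, and it is why the point is put here as a failure to reconcile two rules and not as a flat contradiction. Its weakness is that it leaves the first-significant-time wording, and the condition that no time at all be significant, almost without content. The text never says that it is the intended reading.

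A reader might infer the opposite: that the plan intends a search past a failed 1 h test. Two phrases seem to point that way, but neither establishes it. The sentence that duration waits for onset follows the rule on order within a time point, and may mean only that onset comes first. Dropping times before onset has content even with a 1 h onset, because the SAP 7.1.1 model includes a pre-dose level.

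A reader might also infer that searching would inflate the error rate to about 1 − 0.95³ = 14.3% if the first three times were null. That assumes independent tests of exactly 5% each. The SAP 7.1.1 code uses a diagonal covariance structure with no subject effect. If a subject's scores correlate positively between the two classroom days, the per-time tests are conservative. At an assumed between-day correlation r, the approximate size is 2[1 − Φ(1.96/√(1 − r))]: 1.9% at 0.3, 0.6% at 0.5 and below 0.1% at 0.7. The documents support no inflation figure. What can be said is that the procedure's stated 0.05 control does not cover a search past a failure.

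**Conclusion.** The concern holds as a gap in the rules for the first two secondary objectives. When 1 h fails and a later time is significant, the plan supports both a later onset and no claim, and does not say which applies. The two end-of-effect rules are a plain inconsistency: 11 h against 9 h in the SAP's own example.

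How often the onset gap would matter cannot be stated. The SKAMP effect and SD are redacted, no time-point effects or correlations are given, and the stated 80% power is for the mean score, not for any single time. A reader might go on to fault the chain because it risks losing every controlled claim if 1 h fails. That is a property of any fixed order starting at 1 h, a legitimate design choice, and the fix below leaves it unchanged.

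The primary test, the per-time estimates and confidence intervals, and the Kaplan-Meier analysis of 50% reduction are not affected. The point should be corrected, but it does not threaten the main conclusion.

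**What to change.** Before database lock:

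- Keep the 1 h-first chain. State that an error-controlled onset can only be 1 h, and that any later onset and its duration are descriptive, without a claim at 0.05.
- Align SAP 5 with the SAP 7.1.3.1 end-of-effect rule (last consecutive significant time). That rule matches the worked example and the wording of the sensitivity analysis.
- State the duration rule for any onset time, not only 1 h.
- Say which onset, controlled or descriptive, defines the sensitivity data set, and what is done if onset is none.
- Align the onset wording in Protocol 8.2.2. If only the SAP is changed, update SAP 1.1, which now declares no changes from the protocol.

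This changes wording only and needs no new data. Protocol 9.3.2 lets clarifications and changes of statistical method be made as administrative changes, and SAP 1 foresees a final version before database lock. The downside is that an onset after 1 h would carry no controlled claim.

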7.1 EFFICACY ANALYSES

The primary population for efficacy assessments will be the FAS population. The Completers population will be used to conduct sensitivity analyses. Efficacy summaries will be presented by visit by treatment arm. Variables that are collected in both the Dose-Optimization and double-blind Treatment Periods will be combined on the same table, but no summaries will be presented in the placebo column for the Dose-Optimization Period.

7.1.1 Primary Variable

Data Summaries

Continuous summary statistics will be presented for the mean SKAMP total score for Visits 6 and 7 for the FAS. Similar summaries will be presented for the Completers population.

Primary Efficacy Analysis

A likelihood-based Mixed-effect Model Repeated Measures (MMRM) will be used to assess the primary objective.

In the model, the SKAMP total score for each timepoint will be analyzed with the fixed effects of sequence (two levels), period (two levels), treatment (two levels) and time (10 levels, one for each of 30 minutes prior and 1, 2, 3, 4.5, 6, 7, 9, 10, and 12 hours post dosing) while the repeated measures effect of timepoint will be defined for subject within sequence and ‘Variance Components (VC)’ covariance structure. An example of the SAS procedure to be used is presented below.

```
proc glimmix data=<dataset>;
  class <treatment sequence period timepoint subject>;
  model <SKAMP> = <treatment>
    <sequence>
    <period>
    <timepoint>
```

```
<treatment * timepoint>
/solution ddfm=kr;

random <timepoint> / type=vc subject=<subject * period> residual;
lsmeans <treatment> / pdiff cl alpha=0.05;

estimate 'd-ATS - Placebo' <treatment> -1 1 / cl;
run;
```

Note: *<italics>* identifies where actual variable name substitutions are required.

<sequence> will be required to be defined as <treatment * period> to ensure estimates are obtainable. The two treatment levels will be: d-ATS (5, 10, 15, 20 mg doses combined) and placebo. The treatment * time interaction is included in the model to allow the form of the relationship to be modeled. The purpose of including the interaction term is not to test it for significance and so p-value will not be presented. Raw means, least-squares (LS) means, differences in LS means, and 95% confidence interval (CI) for the difference between treatment arms, and p-values will be calculated for SKAMP total score over the treatment day for the FAS (primary), and Completers populations.

Scaled residual and random effects plots will be considered to check the assumptions behind the mixed model.

Assessment of Carryover

The sequence effect (treatment x period interaction) will be tested at the significance level of 0.10. If significant differences are detected between sequences, data will be reviewed and strength of evidence indicating a crossover effect will be considered. In this case data from Visit 6 only will be presented to aid in assessment of the treatment effect. When only one period of data is used then the efficiencies gained from conducting a crossover trial design may be lost and there is concern associated with treating data as a parallel study due to the sample size being based up on the assumed efficiencies and may no longer be large enough to provide sufficient power. In this case, permutation test will be used to validate the results. Sampling without replacement (i.e. duplicate samples are not allowed) will be performed for 5000 permutations. The average mean treatment difference will be presented along with the associated 95% confidence interval and p-value for the permutation test. This will be compared against a significance level of 0.05.

Effect Modification Analyses

The primary efficacy analysis on the FAS population will also be conducted for the following subgroups:

- Investigator site
- Optimized dose
- Gender
- ADHD type (inattentive, hyperactive/impulsive, combined, not otherwise specified)
- Baseline ADHD severity (defined as the pre-dose ADHD-RS-IV rating scale for Baseline, Visit 0)

- Age group

To ensure summaries from the subgroups are informative, these will only be performed where subgroups include 5 or more subjects in each. Where subgroups have less than 5 subjects the small group will be combined with the next group, if there is a consecutive order to the groupings or with the next smallest group if there is no order. Baseline ADHD-RS-IV total score will be categorized into the following groups: 0-18; 19-36; and 37-54. Age will be categorized into groups for 6-12 years and 13-17 years.

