**8.2 Efficacy Analysis**

The primary population for efficacy assessments will be the FAS population. The Completers population will be used to conduct sensitivity analyses. Efficacy summaries will be presented by visit by treatment arm. Variables that are collected in both the Dose-Optimization and double-blind Treatment Periods will be combined on the same table, but no summaries will be presented in the placebo column for the Dose-Optimization Period.

The mean SKAMP total score will be the average of all SKAMP total scores collected over the course of a laboratory assessment day with the exception of the score from the session prior to dosing. For subjects who started a classroom day but did not complete all the assessments, their last observation within the same classroom will be carried forward for the primary and secondary efficacy analyses. Data from one classroom day will not be used to impute values for the other test classroom day.

Amendment 4: Version 5.0 May-08-2013

Amendment 3: Version 4.0 December-11-2012

Amendment 2: Version 3.0 October-31-2012

Amendment 1: Version 2.0 August-02-2012

Final Protocol May-25-2012

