Age will be calculated as (date of informed consent – date of birth + 1) / 365.25.

Baseline

Baseline is defined as data collected at Visit 0 (Day 0). If data was not collected at Visit 0, the last data available prior to Visit 0 will be used as the baseline data. However during the double

blind crossover phase change from baseline analyses will be performed taking the pre-dose data at the same classroom visit to be the baseline.

Body Mass Index

Body Mass Index (BMI) will be calculated as weight in kg / (screening height in m)².

Prior and Concomitant Medications

Prior medications are defined as those taken prior to the date of first dose of study medication. Concomitant medications are defined as those on or after the date of first dose of study medication through and including the day of the safety follow-up visit. Medications with a missing or incomplete start date will be assumed to be concomitant.

Concomitant medications will be assigned to either the Dose-Optimization Period or the double-blind Treatment Period of the study according to the start date, and will be summarized separately. Concomitant medications for which a missing or incomplete start date makes it impossible to determine which period of the study they started in will be counted as starting in the Dose-Optimization Period.

Treatment-emergent adverse event

A treatment-emergent adverse event (TEAE) is one which first occurs or worsens in severity after the first patch application and not later than 30 days following last patch removal. Adverse events are collected through the last study visit. Those AEs with a start date equal to the date of first patch application will be considered as TEAEs.

Adverse events for which a missing or incomplete start date makes it impossible to determine whether or not they were treatment-emergent will be counted as being treatment-emergent.

Adverse events will be assigned to either the Dose-Optimization Period or the double-blind Treatment Period of the study according to the start date, and will be summarized separately. Adverse events for which a missing or incomplete start date makes it impossible to determine which period of the study it started in will be counted as starting in the Dose-Optimization Period

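### The primary endpoint averages the nine post-dose SKAMP scores, but the SAP's primary contrast averages ten sessions and gives the pre-dose score a weight of 1/10

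*SAP*

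**What the plan says.** SAP 4.1 names the mean SKAMP total score as the primary efficacy measure. Protocol 8.2 defines it as the average over the "laboratory assessment day with the exception of the score from the session prior to dosing", and the definition in SAP section 5 carries the same exclusion. Ten sessions are rated on each classroom day, so the endpoint is the mean of nine.

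The primary model in SAP 7.1.1 takes the score at each session as the response, with "time (10 levels, one for each of 30 minutes prior and 1, 2, 3, 4.5, 6, 7, 9, 10, and 12 hours post dosing". Protocol 8.2.1 lists the same ten levels. The SAP code adds treatment*timepoint and obtains the primary result from an LSMEANS statement on treatment and from "estimate 'd-ATS - Placebo' <treatment> -1 1 / cl". SAP 7.1.3.1 describes that contrast when it explains how to obtain the onset results, by "substituting the estimate statement given (mean estimates across timepoints").

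The gate for the secondary tests is in SAP section 7: "If the primary efficacy endpoint, difference between d-ATS and placebo in mean SKAMP total score for the double-blind phase, is statistically significant", then onset and duration may be tested. SAP section 5 also gives the pre-dose score a different role: in the double "blind crossover phase change from baseline analyses will be performed taking the pre-dose data at the same classroom visit to be the baseline".

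**The concern.** The endpoint gives the pre-dose session weight 0; the coded contrast gives it the same weight as every other session. The quantity that opens onset and duration testing is therefore not quite the quantity the plan defines. One section treats the pre-dose score as a baseline, while another averages it into the outcome.

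Three things are at stake:

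- The primary estimate and its interval would be labelled as the mean SKAMP total score while describing a slightly different average.
- The descriptive summary of the defined mean and the model-based difference would target different quantities in the same report.
- The multiple-imputation and LOCF analyses in SAP 7.1.2 refer back to the 7.1.1 method, so they inherit the same weight and would not reveal the mismatch.

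If the discrepancy were noticed only after unblinding, someone would have to choose between a nine-session and a ten-session primary result.

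**Working it through.** **The plan's own figure.** SAP 3.1 states 74 completers for 80% power at two-sided 0.05. The SD and the difference are redacted, so 74 cannot be reproduced. For a paired comparison it implies a standardised difference of (1.960 + 0.842)/√74 = 2.802/8.602 = 0.326. The weights below do not depend on it.

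**Weights.** Let D_t be the d-ATS minus placebo difference at session t, D_pre the pre-dose difference, and D_post = (1/9) × the sum of the nine post-dose D_t.

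- Defined endpoint: 0 × D_pre + 1 × D_post.
- Coded contrast: with treatment*timepoint in the model and no interaction coefficients supplied, LSMEANS and ESTIMATE spread the interaction evenly over the ten levels. The result is (1/10)(D_pre + 9 × D_post) = 0.9 × D_post + 0.1 × D_pre.

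As a check, the SAP's fixed effects (sequence entered as treatment*period) were fitted by least squares to a layout of 90 subjects, two periods and ten sessions. Each session received weight 0.1000, both with complete data and with up to 30% of late sessions missing.

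**Size relative to the endpoint.** Write D_pre = r × D_post. The contrast is then (0.9 + 0.1r) × D_post.

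| r | Coded contrast ÷ defined endpoint |
|---|---|
| −0.5 | 0.85 |
| 0 | 0.90 |
| +0.5 | 0.95 |
| +1 | 1.00 |

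A noise-free fit with D_post = −1 returned −0.85, −0.90, −0.95 and −1.00. The contrast with 0 on pre-dose and 1/9 on each post-dose session is estimable and returned −1.00 every time.

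**What is known of D_pre.** Protocol 5.1 has patches applied at about 8:00 and removed after 9 hours, so at about 17:00. If clinic dosing is at a similar hour, a session in the 30 minutes before dosing falls about 14.5 to 15 hours after the last removal. The 12-hour session falls 3 hours after removal. Each classroom day also follows six days on the assigned treatment. None of this fixes D_pre.

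**Power, as illustration only.** Assume the planned 80% refers to the nine-session mean, unit variances for the subject-level treatment differences, post-dose correlation p, pre/post correlation c, and a valid standard error. Then:

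- V9 = (9 + 72p)/81
- V10 = (10 + 72p + 18c)/100
- k = (0.9 + 0.1r) × √(V9/V10)
- power = Φ(2.802k − 1.960)

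With p = 0.8, V9 = 66.6/81 = 0.822.

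| r | c | V10 | k | Power |
|---|---|---|---|---|
| 0 | 0.8 | 0.820 | 0.901 | 71.4% |
| 0 | 0 | 0.676 | 0.993 | 79.4% |
| +0.5 | 0 | 0.676 | 1.048 | 83.5% |

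The sign of the change depends on inputs the documents do not give. These figures are neither bounds nor the power of the variance-components model as written.

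**The protocol's version.** Protocol 8.2.1 lists sequence, period, treatment and time, with no treatment-by-time term. That model has one treatment effect common to all ten sessions. With complete data pre-dose again has weight 0.10. When later sessions are missing (the same pattern, up to 30%) its weight rises to about 0.12. A post-dose contrast cannot be formed there at all.

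**The case against.** The best defence is that the endpoint itself is not in doubt. The gate names the mean SKAMP total score, and that term is defined without pre-dose. The code is offered as an example, and SAP 7.1.3.1 promises that "p-values will be calculated for each post-dose time point and for mean score over the treatment day for the FAS population", which could be read as the nine-session mean. All nine post-dose differences are to be reported as well, so a reader could average them and recover the intended point estimate.

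Part of this stands. The fault lies in the analysis specification, not in the definition, and the harm is limited because 90% of the weight is on the stated endpoint. But the ten levels are in the body text of both documents, not only in the code, and the SAP's own prose describes the contrast as a mean across timepoints. Averaging nine reported differences gives an estimate but not the interval or the p-value that operates the gate. The sensitivity analysis in SAP 7.1.3.1 that drops sessions before onset and after the end of effect is not a remedy: its sessions are chosen by the observed results, and it can remove post-dose sessions too.

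A reader might go further and infer that the primary test is invalid, that power falls by a known amount, or that the pre-dose difference must be zero. The documents support none of these. If no session has a treatment effect, both D_pre and D_post are zero and so is the contrast, so the extra weight does not inflate type I error. The power change cannot be determined and may be a gain. Six days on the assigned treatment mean that a non-zero pre-dose difference cannot be excluded. Nor would exact agreement between model and raw differences follow from D_pre = D_post, since missing sessions and unequal sequence sizes can separate them.

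**Conclusion.** The concern holds. As SAP 7.1.1 is written, the primary estimate, interval and gating p-value target 0.9 × D_post + 0.1 × D_pre, not the defined post-dose mean. The 1/10 weight follows from the SAP's model and the default behaviour of the two statements; it needs no assumption about the data. The consequence does need one: the estimate is 10% too small if D_pre = 0, correct if D_pre = D_post, and 85% to 95% of the endpoint for D_pre between −0.5 and +0.5 times D_post. The effect on power is undetermined.

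The onset and duration estimates at each session are not affected, although whether they are formally tested depends on the gate. The point should be fixed before unblinding because it sits in the gating test and is cheap to correct.

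**What to change.** In SAP 7.1.1, keep the ten-level model with treatment*timepoint and replace the primary contrast with one that gives pre-dose zero weight. With pre-dose as the first time level and the SAP's treatment order:

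`treatment -9 9, treatment*timepoint 0 -1 -1 -1 -1 -1 -1 -1 -1 -1 0 1 1 1 1 1 1 1 1 1 / divisor=9 cl`

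Report the treatment LS-means with the same weights, since LSMEANS on treatment would otherwise use 1/10 for each session. Add a sentence stating that the primary contrast is the mean over the nine post-dose sessions. Use the same contrast in the multiple-imputation, LOCF and worst-case analyses of SAP 7.1.2.

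In protocol 8.2.1 the contrast cannot simply be inserted. Either add the treatment-by-time interaction together with the post-dose contrast, or drop pre-dose from the response. Otherwise, record the difference in SAP 1.1, which now declares no changes from the protocol. For PERMP (SAP 7.1.3.2), only confirm that any day-average uses the post-dose sessions.

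The cost is low: one ESTIMATE statement, matching LS-means weights and a few sentences. Data collection does not change.
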